8.7.2 Method of Detecting AEs and SAEs

Care will be taken not to introduce bias when detecting AEs and/or SAEs. Open-ended and non-leading verbal questioning of the patient is the preferred method to inquire about AE occurrences.

8.7.3 Follow-up of AEs and SAEs

After the initial AE/SAE report, the Investigator is required to proactively follow each patient at subsequent visits/contacts. All SAEs, will be followed until resolution, stabilization, the event is otherwise explained, through the follow-up contact, or the patient is lost to follow-up (as defined in Section 7.4). Further information on Follow-up of AEs and SAEs is given in Section 11.7.

8.7.4 Regulatory Reporting Requirements for SAEs

- Prompt notification by the Investigator to the Sponsor of an SAE is essential so that legal obligations and ethical responsibilities towards the safety of patients and the safety of a blinded study medication under clinical investigation are met.
- The Sponsor has a legal responsibility to notify both the local regulatory authority and other regulatory agencies about the safety of a blinded study medication under clinical investigation. The Sponsor will comply with country-specific regulatory requirements relating to safety reporting to the regulatory authority, Institutional Review Boards (IRB)/Independent Ethics Committees (IEC), and Investigators.
- Investigator safety reports must be prepared for suspected unexpected serious adverse reactions (SUSAR) according to local regulatory requirements and Sponsor policy and forwarded to Investigators, as necessary.
- An Investigator who receives an Investigator safety report describing an SAE or other specific safety information (e.g. summary or listing of SAEs) from the Sponsor will review and then file it along with the IB and will notify the IRB/IEC, if appropriate according to local requirements.

8.7.5 Pregnancy

- Details of all pregnancies in female patients will be collected after the start of blinded study medication and until 30 days after the last dose of blinded study medication.
- If a pregnancy is reported, the Investigator should inform the Sponsor within 24 hours of learning of the pregnancy and should follow the procedures outlined in Section 11.8.
- Abnormal pregnancy outcomes (eg spontaneous abortion, fetal death, stillbirth, congenital anomalies, ectopic pregnancy) are considered SAEs.

8.7.6 Adverse Events of Special Interest

Adverse events of special interest have not been identified for ensifentrine.

8.7.7 Disease-related Events and/or Disease-related Outcomes Not Qualifying as AEs or SAEs

COPD exacerbations are an expected disease-related outcome. COPD exacerbations will not be collected as an AE unless they meet the definition of an SAE. COPD exacerbations should be captured on the COPD exacerbation eCRF (Section 11.6).

8.7.8 Medical Device Incidents (Including Malfunctions)

The PARI LC Sprint nebulizer and PARI Vios PRO Aerosol Delivery System, and PARI BOY compressor or equivalent are being provided for use in this study for administration of blinded study medication.

In order to fulfill regulatory reporting obligations worldwide, the Investigator is responsible for the detection and documentation of events meeting the definitions of incident or malfunction that occur during the study with such devices.

The definition of a medical device incident, examples of incidents, and instructions for documenting and reporting medical device incidents are provided in Section 11.10.

Medical Device incidents fulfilling the definition of an AE/SAE will also follow the processes outlined in Section 11.7.

8.7.8.1 Time Period for Detecting Medical Device Incidents

- Medical device incidents or malfunctions of the device that result in an incident will be detected, documented, and reported during all periods of the study in which the medical device is used.
- If the Investigator learns of any incident at any time after a patient has been discharged from the study, and such incident is considered reasonably related to a medical device provided for the study, the Investigator will promptly notify the Sponsor.
- The method of documenting Medical Device Incidents is provided in Section 11.10.

8.7.8.2 Follow-up of Medical Device Incidents

- All medical device incidents involving an AE will be followed and reported in the same manner as other AEs (Section 11.7). This applies to all patients, including those who discontinue blinded study medication.
- The Investigator is responsible for ensuring that follow-up includes any supplemental investigations as indicated to elucidate the nature and/or causality of the incident.
- New or updated information will be recorded on the originally completed form with all changes signed and dated by the Investigator.

8.7.8.3 *Prompt Reporting of Medical Device Incidents to Sponsor/Sponsor Representative*

- Medical device incidents will be reported to the Sponsor/Sponsor's designee within 24 hours after the Investigator determines that the event meets the protocol definition of a medical device incident.
- The Medical Device Incident Report Form will be sent to the Sponsor/Sponsor's designee by the same method as used for SAE reporting (Section 11.7).
- Contacts for Medical Device Incident reporting are the same as SAE reporting and can be found in Section 11.2 on the Medical Monitor Contact Information Page.

8.7.8.4 *Regulatory Reporting Requirements for Medical Device Incidents*

- The Investigator will promptly report all incidents occurring with any medical device provided for use in the study in order for the Sponsor/Representative to fulfill the legal responsibility to notify appropriate regulatory authorities and other entities about certain safety information relating to medical devices being used in clinical studies.
- The Investigator, or responsible person according to local requirements (eg, the head of the medical institution), will comply with the applicable local regulatory requirements relating to the reporting of incidents to the IRB/IEC.

8.7.9 *COVID-19 Positive for Active Disease*

An AE/SAE of positive COVID-19 active disease should be documented as any AE/SAE occurring in this study would be documented per the guidance throughout this (Section 8.7). In addition, local guidelines for reporting COVID-19 to local and/or health authorities should be followed.

8.8 *Treatment of Overdose*

An overdose is defined as a dose greater than the total daily doses prescribed in this study which results in clinical signs and symptoms. These should be recorded by the investigator on the AE/SAE pages.

In the event of an overdose the investigator should use clinical judgement in treating the overdose and contact the study Medical Monitor. Verona Pharma is not recommending specific treatment guidance for overdose and toxicity management.

9.0 STATISTICAL CONSIDERATIONS

9.1 Statistical Hypotheses

The aim of this study is to show superiority of ensifentrine over placebo regarding selected efficacy measures. The null hypothesis to be tested for each endpoint will be that there is no difference between ensifentrine and placebo, against the alternative hypothesis that ensifentrine is better than placebo. All tests will be two-sided at a 5% significance level. Primary and key secondary endpoints used for claims will be tested in a sequential order to preserve the alpha level. Testing will stop once a not significant result is achieved. Test order will be FEV₁ AUC_{0-12h} at 12 weeks, peak FEV₁ at 12 weeks, weekly mean E-RS total symptom score at week 24, SGRQ total score at 24 weeks, morning trough FEV₁ at Week 12, FEV₁ AUC_{0-4h} at 12 weeks and proportion of SGRQ responders at Week 24.

9.2 Sample Size Determination

Approximately 800 patients will be randomized. The standard deviation for the change in FEV₁ AUC_{0-12h} is estimated to be 250 mL. With a 2-sided test at a 5% significance level and 500 vs. 300 evaluable patients in the two groups, there will be an 90% power to detect a true difference of 59 mL between the treatments. If the withdrawal rate at 24 weeks exceeds 25% overall, additional patients may be randomized to the study to compensate for the loss of data.

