Overall, 500 patients will be randomized to ensifentrine and 300 patients will be randomized to placebo.

All blinded study medications will be double-blind and administered using the inhaled route via a standard jet nebulizer supplied by the Sponsor. Nebulization time should be approximately 5 minutes but no longer than 10 minutes.

Statistical Methods

Efficacy analysis will primarily be performed on the modified intent-to-treat (mITT) population including all patients randomized and treated in the study. All tests will be two-sided at a 5% significance level. Secondary efficacy endpoints intended for label claims will be tested in a strict hierarchical order to preserve the alpha level.

Primary endpoint, change from baseline in FEV₁ AUC_{0-12h} at Week 12, will be compared between treatments using an analysis of covariance (ANCOVA) model adjusting for treatment, region, background medication strata, smoking status, and baseline FEV₁. Patients will be included in analysis as randomized. Missing data will be imputed to get as close to the mITT population as possible. Primary choice of imputation will be based on data collected at early termination visits or at visits performed after treatment withdrawal and, when no such data available, by the average change in the opposite treatment group as randomized to.

[figure not shown]
Safety analysis will be descriptive and based on the safety set including all randomized and treated patients. Safety analysis will be by actual treatment received.

Sample Size

Approximately 800 patients will be randomized. The standard deviation for the change in peak FEV₁ is estimated to be 250 mL. With a 2-sided test at a 5% significance level and 500 vs. 300 evaluable patients in the two groups, there will be an 90% power to detect a true difference of 59 mL between the treatments.

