4.2. INTERIM ANALYSIS

There is no interim analysis planned for this study, however additional patients may be randomized if:

- the SD has increased significantly from the estimated 250 mL, as per sponsor discretion, and/or
- the withdrawal rate at 24 weeks exceeds 25% overall, and the percentage of patients with missing FEV₁ over 12 hours at Week 12 in mITT (modified Intent-to-Treat) population exceeds 20% overall.

Note: As part of the primary endpoint analysis, SD of the treatment difference is calculated to check the sample size with 90% power.

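### The stated 90% power for 59 mL has no allowance for missing Week 12 data; at the SAP's own 20% missing-data limit it is about 82%

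*Protocol*

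**What the plan says.** Protocol 9.2 bases its calculation on "500 vs. 300 evaluable patients in the two groups" and a two-sided 5% test. Its variability input reads: "The standard deviation for the change in FEV₁ AUC_{0-12h} is estimated to be 250 mL". From these inputs the section concludes that "there will be an 90% power to detect a true difference of 59 mL between the treatments". The planned total is about 800, and the synopsis (Protocol 1.1) splits it between the arms: "Overall, 500 patients will be randomized to ensifentrine and 300 patients will be randomized to placebo".

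Protocol 9.2 then allows more patients to be randomised if withdrawal at 24 weeks is above 25%. SAP 4.2 narrows that route to two conditions that must both hold. One is that "the withdrawal rate at 24 weeks exceeds 25% overall"; the other is that more than 20% of the mITT population lack the 12-hour FEV1 at Week 12. A separate trigger in SAP 4.2 concerns an increase in the SD. In every case the addition is optional.

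The Sample Size paragraph of the synopsis repeats the 250 mL and 59 mL figures but attaches them to another variable. The sentence there opens "The standard deviation for the change in peak", so it refers to peak FEV1. The primary endpoint in both documents is average FEV1 AUC0-12h at Week 12.

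**The concern.** The evaluable numbers in the power statement equal the numbers randomised, so the calculation assumes that every randomised patient contributes a Week 12 AUC0-12h. The same paragraph foresees loss of data, and the SAP sets the point at which that loss would be acted on. A reader of 9.2 would take 90% as the power of the planned trial, although the plan accepts without action a level of missing data at which power is materially lower. The synopsis also leaves unclear which endpoint was powered.

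**Working it through.** **Inputs.** SD 250 mL, difference 59 mL, two-sided 5%, 500 vs 300 evaluable (Protocol 9.2); 500 and 300 randomised (Protocol 1.1); 20% missing Week 12 12-hour FEV1 and 25% Week 24 withdrawal (SAP 4.2).

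**Formulas.** With a fraction L of each arm missing:

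- SE = 250 × √[(1/500 + 1/300)/(1 − L)]
- Power ≈ Φ(59/SE − 1.96)
- Difference detectable with 90% power = (1.96 + 1.2816) × SE

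**The plan's own figure.** With L = 0, SE = 250 × √0.005333 = 18.26 mL. 59/18.26 = 3.232, and Φ(3.232 − 1.96) = 89.8%. The detectable difference is 3.2416 × 18.26 = 59.2 mL. The stated 90% for 59 mL is reproduced. There is no slack: a full 90% needs about 302 + 503 = 805 evaluable patients.

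**With missing data.**

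| Missing | Evaluable | SE (mL) | Power, normal | Power, noncentral t | Detectable with 90% power |
|---|---|---|---|---|---|
| 0% | 500 vs 300 | 18.3 | 89.8% | 89.8% | 59.2 mL |
| 10% | 450 vs 270 | 19.2 | 86.6% | 86.5% | 62.4 mL |
| 20% | 400 vs 240 | 20.4 | 82.4% | 82.3% | 66.2 mL |
| 25% | 375 vs 225 | 21.1 | 79.9% | 79.8% | 68.3 mL |

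**Why imputation does not close the gap.** The primary imputation model (SAP 16.1.2) contains treatment, region, the two strata, baseline FEV1 and the Week 12 AUC0-12h itself, with no intermediate visits. Under missing at random it adds essentially nothing to what the ANCOVA already draws from the observed patients.

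**Sensitivity to the SD.** The documents do not say whether 250 mL is an unadjusted or a residual SD. If it is unadjusted and the covariates explain a fraction R² of the variance (an assumption), SE is multiplied by √(1 − R²). With R² = 0.10 the SD becomes 250 × √0.90 = 237 mL, and power is 86.1% at 20% missing and 83.9% at 25%. The adjustment cancels the loss when R² = L, so 0.20 is needed at 20% missing and 0.25 at 25%.

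**Sensitivity to uneven loss.** With 20% missing overall but 30% on placebo (430 vs 210), power is 80.0%.

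**The case against.** **The condition is already printed.** Protocol 9.2 says evaluable, so the 90% is correct as worded. That stands: this is not an arithmetic error. The gap is that no allowance connects the evaluable number to the identical randomised number.

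**The 25% figure is not endpoint loss.** A reader might infer that 25% withdrawal means 25% missing primary data, and hence 80% power. The documents do not support that. The 25% is withdrawal by Week 24, the endpoint is at Week 12, and the SAP counts missing 12-hour FEV1 separately. Patients who leave after Week 12 can already have contributed the endpoint. For those withdrawn earlier, Protocol 7.3.1.1 asks for every effort to obtain 12-hour spirometry, although it is optional for patients already off drug. SAP 6.4 uses such data whenever they were collected. As an illustration (assumed), if 25% withdraw and half do so before Week 12 without usable data, 12.5% are missing and power is about 85.6%. If half of those supply early-termination spirometry, 6.25% are missing and power is about 87.9%. The 25% case is allowed only because the SAP joins its conditions with 'and': missing data above 20% trigger nothing while withdrawal is at or below 25%. It is a limit, not a forecast.

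**Other safeguards exist.** Blinded monitoring (Protocol 9.5) and the SD trigger (SAP 4.2) help to protect power, but the SD trigger does not respond to attrition.

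**The trial may still be well powered.** A reader might infer an underpowered trial. Nothing in the documents makes 59 mL the expected or the minimum important effect. Protocol 2.2 reports 87 mL for average FEV1 over 12 hours with 3 mg at Week 4 in the tiotropium add-on study. At 87 mL, power is 98.9% with 20% missing and 98.5% with 25%.

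**Conclusion.** The point holds as a shortcoming of the power statement. The 90% for 59 mL requires a Week 12 AUC0-12h from all 800 randomised patients. At the SAP's 20% missing-data limit, power is about 82% and the difference detectable with 90% power is about 66 mL. This is the main result, since 20% is the plan's own figure for the primary measurement. At 10% missing, power is about 86.5%. About 80% (68 mL) at 25% missing is the extreme case; actual Week 12 loss should be lower. The figures assume a residual SD of 250 mL, a true difference of 59 mL and equal loss by arm. An unadjusted SD would make them pessimistic, and heavier loss on placebo would make them optimistic. The peak FEV1 wording in the synopsis is a separate slip that leaves the arithmetic unchanged.

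**What to change.** In Protocol 9.2 and the synopsis:

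- State that 90% power for 59 mL in FEV1 AUC0-12h requires all 800 patients to be evaluable at Week 12.
- Add the power at 10% missing Week 12 data (about 86.5%) and at 20% (about 82%, or 90% for about 66 mL), with 25% (about 80%, or 90% for about 68 mL) marked as the extreme case.
- Say whether 250 mL is an unadjusted or a residual SD. If the plan relies on covariate adjustment to absorb loss, give the assumed R² and recompute these figures.
- In the synopsis, replace peak FEV1 with FEV1 AUC0-12h.

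The cost is a few sentences and a less favourable power figure. Sample size and analysis do not change, and no extra patients are needed.

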9.3 Populations for Analyses

mITT population: will include all patients randomized and treated with blinded study medication in the study. Patients will be handled as randomized in the mITT analyses.

PP population: will include all patients in the mITT without any major/important protocol deviations considered to have an impact on efficacy assessments. Reasons for exclusion will be specified at a Blind Data Review Meeting prior to database lock (DBL) and may include violations of inclusion/exclusion criteria, violations of withdrawal criteria, incorrect randomization, use of prohibited medication and non-compliance.

Safety set: will include all patients randomized and treated in the study. Patients will be handled by actual treatment in the safety analyses.

9.4 Statistical Analyses

9.4.1 Efficacy Analyses

Efficacy analysis will primarily be performed on the mITT population. The primary endpoint and key secondary endpoints will also be evaluated using the PP population as a sensitivity analysis. Impact of imputations and various baseline characteristics will also be checked.

The primary endpoint, change from baseline in FEV₁ AUC_{0-12h} at Week 12, will be compared between treatments using an analysis of covariance (ANCOVA) model adjusting for treatment, region, background medication strata, and smoking status as factors and baseline FEV₁ as covariate. The estimated treatment difference with 95% confidence interval and associated (two-sided) p-value will be presented. Missing data will be imputed to get as close to the mITT population as possible. Primarily imputation will be based on data collected at visits performed after treatment withdrawal or at early termination visits even if outside the visit window. When no such data is available, imputation will primarily be done using multiple imputation based on baseline characteristics and secondarily, as a sensitivity analysis, by the average change in the opposite treatment group as randomized to as a worst-case scenario. Further details on the handling of missing data will be given in the Statistical Analysis Plan.

Key secondary endpoints, FEV₁ AUC_{0-4h}, peak FEV₁, morning trough FEV₁, SGRQ total score and weekly mean E-RS total score, and other continuous secondary or exploratory endpoints will be assessed repeatedly during the study and the change from baseline to pre-specified time point of evaluation will be compared by similar ANCOVA models adjusting for treatment, region, background medication strata and smoking status as factors and baseline as covariate. Data collected at visits performed after treatment withdrawal or at early termination visits will be used in the analyses. Remaining missing data will primarily be imputed using multiple imputation based on baseline characteristics and data collected at post-randomization visits. Since assessed repeatedly, in contrast to primary endpoint, these data will also be analyzed for sensitivity by mixed model repeated measures models with treatment, visit and treatment by visit interaction as factors, baseline as covariate, subject as random factor and covariance structure by visit.

The proportion of responders on the SGRQ, patients with an improvement of at least 4 units, will be compared between treatment groups using a logistic regression model with fixed factors treatment, region, and background medication strata, and smoking status. Imputation of missing data will be done similar as for continuous endpoints. A sensitivity analysis will be performed in which patients with missing data at the required visit will be considered a non-responder in the analysis.

The time to first COPD exacerbation during the 24 or 48 week treatment period, depending on stratification, will be visualized using a Kaplan-Meier plot and compared between treatment groups using the log-rank test, stratified by region, background

medication strata, and smoking status. As a secondary evaluation a Cox's proportional hazards model will be used with the same factors. Patients without exacerbations will be censored at last day in the treatment period, including period of recording after possible treatment withdrawal. The treatment difference in the Cox model will be expressed as a hazard ratio. Assumption of proportional hazards will be checked. The number of COPD exacerbations during the 24- or 48-week treatment period will be compared between treatments using a negative binomial model adjusting for treatment, region, background medication strata and smoking status and further using the log exposure time as an offset. The treatment difference from the negative binomial model will be expressed as an annualized risk ratio.

Subgroup analyses will be performed for the primary endpoint and selected secondary endpoints by gender, age-class (below or above 65 years), region, background medication strata, smoking status, ICS use, known chronic bronchitis, and FEV₁ reversibility at baseline ($\geq 12\%$ and ≥ 200 mL).

9.4.2 Safety Analyses

Safety analysis will be based on the safety set.

Adverse events will be analyzed using quantitative and qualitative measures. Treatment-emergent adverse events will be summarized by treatment group for all AEs, related AEs, serious adverse events, deaths, adverse events leading to discontinuation of blinded study medication or to withdrawal from study, adverse events of different severity and adverse events of different chronicity. Treatment-emergent adverse events will be coded using the Medical Dictionary for Regulatory Activities (MedDRA) and summarized by system organ class and preferred term for each treatment group. For selected adverse events, time to first event will be visualized using Kaplan-Meier plots.

Laboratory data will be summarized by each visit including change from baseline. The number of normal, abnormal not clinically significant and abnormal clinically significant values on each parameter will be summarized for change over study using shift tables. All data will be listed and values outside reference ranges will be highlighted in the listings.

Vital signs and continuous parameters from the ECGs will be summarized by each visit including change from baseline. Values outside pre-specified ranges (low, high) or changes exceeding pre-specified limits will be summarized by visit for each parameter. The number of normal, abnormal not clinically significant and abnormal clinically significant values on the ECG overall evaluation will be summarized for change over study using shift tables. All data will be listed and values outside reference ranges will be highlighted in the listings.

